3.0 Intervention to be studied

The two interventions to be studied are: 1) DWN-FIT and 2) DWN-FIT_Social Support.

Components of Digital Intervention for DWN-FIT and DWN-FIT_Social Support:

Cognitive Behavioral Skills Training (CBST) Video Modules: Every week a group of 3 - 5 videos will be made available to the AAAO and their caregiver, no longer than 5-minutes in length. Videos are based on the mandatory modules used within FIT Families. These instructional modules will be translated to scripts and scenes with the guidance of [name] (Consultant and FIT Families Co-I).

The proposed schedule is as follows:

- Week 0 – DWN-FIT Orientation and Getting Started on the Mobile App
- Weeks 1-2 – physical activity (PA) education
- W3-4 – nutrition education
- W5-6 - parenting strategies (only available to caregiver) and self-monitoring (SM)
- W7-8 - environmental control of nutrition and PA
- W9-10 - managing hunger
- W11-12 - managing cravings

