Self-Monitoring (SM) Assessments: Throughout the study, participants will complete assessments via the conversational interface of the mobile app. At the beginning of the intervention (T0), participants will complete a baseline assessment focused on their current engagement in- and perception of-healthy behaviors (eating habits and physical activity level). This assessment will be adapted from the Patient Health Engagement (PHE) Scale⁴⁸. The same questions regarding patient engagement will also be asked at each assessment time point (T1 – T3). The DWN will prompt the participants daily to use the SM feature of the mobile app to complete an assessment that will determine their daily implementation of the physical activity tasks and cognitive behavioral skills learned. For example, participants will be asked to complete a food log that documents the amounts of fruits and vegetables, junk food, water, protein, and whole grains consumed each day. These food types and their suggested quantities are detailed in the nutrition education learning modules. The DWN will also conduct weekly assessments, initially only asking participants to weigh themselves and record their body fat. As the intervention progresses, in collaboration with the CHW they will also be asked to set their weekly treatment goals and reflect on their goals from the past week (barriers that prevent them from reaching their goals and if they need to modify their goals). As a part of SM component, the caregiver and CHW are notified when the AAAO submits or misses submitting an assessment. Once an assessment is submitted, the caregiver reviews the adolescent's progress. If the AAAO does not submit the required assessment or if the caregiver does not review one, the CHW is alerted, and they have the option to reach out directly to the participants through the messaging feature.

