9.0 Study Design / Methods

Study participation will last 3 months. Families who consent to participate will be instructed to download the DWN app and complete a demographics survey. The research assistant will schedule the first session with the CHW and mail the weight scale, yoga mat, resistance bands, and Fitbit Inspire 3s to the family. Families will be randomly assigned to one of two intervention groups: the DWN-FIT or the DWN-FIT_Social Support (SS) group. CHWs will meet with families once a week for 3 months via video chat interface on the DWN-FIT app. The sessions will last approximately 45-minutes to 1 hour and will include: 1) review of SM goals; 2) review of PA steps and calories burned; 3) goal setting based on assessments and learning modules; and 4) review of CBST learning modules using evidence-based steps for skill acquisition (discussion of rationale, modeling of skill, caregiver and AAAO behavioral rehearsal of skill, feedback), and caregiver and AAAO develop implementation plans for between session skills practice.

We will also conduct a focus group with the participants after W12 of the study. These 17 focus groups (16 with participants and support person and 1 with all CHWs) will be guided by the responses to the needs analysis and usability evaluation; however, the questions will be open-ended to encourage discussions to obtain a fuller understanding of their personal experiences using the DWN. We will subsequently transcribe the audio recordings and group the data based on the discussion questions. Then, we will use either an inductive thematic analysis or a bottom-up technique to identify themes or recurring patterns in the responses. Caregivers, AAAOs, Supporters, and CHWs will be compensated \$195.55 for participating in a focus group.

Aim 1: Feasibility Testing. Evaluate the DWN-FIT intervention (delivered by 2 CHWs) with 16 families (AAAO and caregiver, overweight or obese) undergoing treatment for adolescent obesity to determine the degree to which the components of the digital intervention are correlated with adolescent-caregiver engagement in healthy behaviors and adherence to the prescribed treatment. Additionally, we will determine the degree to which SS, as an additional element of DWN-FIT, enhances engagement and retention of families within treatment.

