Methods: This aim follows two conditions (DWN-FIT vs DWN-FIT_Social Support [SS]) x 4 time (T0: baseline, T1: 1-month follow-up, T2: 2-month follow-up, and T3: 3-month end of treatment), with random assignment of 16 families (caregivers/AAAO) to one of the two treatment conditions. The proposed 3-month treatment period is too short to assess the feasibility of this digital treatment with respect to weight loss measurements (secondary outcomes), so instead we will assess feasibility of this approach based on the development of healthy behaviors (primary outcomes) that have been shown to lead to sustainable weight loss over time. Primary outcomes will be measured after each session (weekly) through the data recorded by the DWN app. These primary measures consist of the following measurements via the DWN app: step count, PA and PA video views, frequency and consistency of nutrition SM, messaging read and response rates, frequency and consistency of CBST education participation, telehealth session attendance, and CM rewards. In both treatment conditions, we will determine correlation between these measures and our measures of engagement and adherence. We will also determine the effect of semi-automated SS on each of the measures by comparing outcomes from each treatment group (DWN-FIT vs DWN-FIT_SS). Caregiver and AAAO percent

overweight and body-mass index (BMI) will serve as secondary outcome measures and will be collected each week via a provided digital scale. These secondary outcomes will be used to build preliminary data for a future full time-course (6-month or greater) randomized clinical trial (RCT).

Measures: We will measure **engagement** through the delivery of the 9-item Patient Health Engagement (PHE)⁴⁸ survey. The PHE is used to determine the degree to which patients are engaged in their own health and describes the patient's ability to manage their own health. PHE has been validated in other work, but a sample size large enough to meet this threshold is outside the scope of this study. The PHE outcomes gathered here will be used as preliminary data for future studies. The PHE survey will be taken via the DWN app at each time point, T0-T3. We will measure **adherence** through comparing the prescribed tasks against the task completed, raw counts (video views, SM entries, PA participation), by each set of participants. We will explore how SS is correlated with adherence to the prescribed treatment.

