Aim 2: Patient Centered Evaluation. Conduct a needs analysis before the intervention, a usability evaluation during the intervention and focus groups with participants after the intervention to determine if DWN met their needs for accessing (participants), delivering (CHWs), and providing support during the treatment.

Needs Analysis: We will develop a pre-survey (at T0 guided by [name]) consisting of a set of qualitative questions that determine the participants' goals and needs related to accessing, delivering, and providing support during the treatment. After completion of the intervention (T3), we will conduct a post-survey to determine if DWN-FIT met their needs and goals. Using responses from these two surveys, we will perform an inductive thematic analysis or a bottom-up technique to identify themes or recurring patterns in participants' responses.

Usability Evaluation: We will deliver a usability assessment via the System Usability Scale (SUS)⁴⁹ assessment that will be delivered to the participants at the midpoint of the intervention; it will focus on the efficiency and effectiveness of accessing, delivering, and providing support during the treatment including such topics such as readability, technology literacy, and interface design.

Construct	Measure / Items	Information / Data Source	When Completed*													
			0	1	2	3	4	5	6	7	8	9	10	11	12	13-16
Eligibility/Screening Criteria																
%Overweight	• Body Mass Index (BMI; height and weight measurements)	Youth & CGs	✓													
Primary Outcome Measure																
% Body Fat	• Bioelectrical impedance analysis (BIA)	Youth & CGs		✓	✓	✓	✓	✓	✓	✓	✓	✓	✓	✓	✓	✓
Secondary Outcome Measure																
Physical Activity (PA)	• Fitbit Inspire 2 accelerometer	Youth & CGs		✓	✓	✓	✓	✓	✓	✓	✓	✓	✓	✓	✓	✓
	• Fitbit data	Youth & CG Fitbit		✓	✓	✓	✓	✓	✓	✓	✓	✓	✓	✓	✓	✓
Self-Monitoring of Dietary Intake	• Food/Beverage Log	Youth & CGs		✓	✓	✓	✓	✓	✓	✓	✓	✓	✓	✓	✓	✓
Clinical Note	• Meeting participants	CHW		✓	✓	✓	✓	✓	✓	✓	✓	✓	✓	✓	✓	✓
	• Meeting Duration	CHW		✓	✓	✓	✓	✓	✓	✓	✓	✓	✓	✓	✓	✓
	• Learning module content review	CHW		✓	✓	✓	✓	✓	✓	✓	✓	✓	✓	✓	✓	✓
	• % body fat	CHW		✓	✓	✓	✓	✓	✓	✓	✓	✓	✓	✓	✓	✓
	• Pregnancy screening question	CHW		✓	✓	✓	✓	✓	✓	✓	✓	✓	✓	✓	✓	✓
	• General notes	CHW		✓	✓	✓	✓	✓	✓	✓	✓	✓	✓	✓	✓	✓
Daily Activity Summary	• Food Log Completion	Youth & CGs	✓	✓	✓	✓	✓	✓	✓	✓	✓	✓	✓	✓	✓	✓
	• Number of Steps Taken	Youth & CGs	✓	✓	✓	✓	✓	✓	✓	✓	✓	✓	✓	✓	✓	✓

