	• Number of calories burned	Youth & CGs	✓	✓	✓	✓	✓	✓	✓	✓	✓	✓	✓	✓	✓	✓
	• Time spent on learning modules	Youth & CGs	✓	✓	✓	✓	✓	✓	✓	✓	✓	✓	✓	✓	✓	✓
	• Messaging	Youth & CGs	✓	✓	✓	✓	✓	✓	✓	✓	✓	✓	✓	✓	✓	✓
Patient Engagement	• Patient Health Engagement (PHE) Survey	Youth & CGs		✓				✓				✓				✓
Eligibility	• Pregnancy (asked by CHW)	Youth & CGs		✓	✓	✓	✓	✓	✓	✓	✓	✓	✓	✓	✓	✓
Demographics	• Family Information Form	Youth, CGs, CHWs	✓													
Qualitative Interview (Focus Groups)	• Gather information on experiences with research and treatment procedures	Youth, CGs, CHWs														✓
Other Measures:																
Mid-Treatment Usability Study	System Usability Scale (SUS) Questionnaire	Youth, CGs, CHWs							✓							
Needs Assessment	Application Needs Pre-Assessment	Youth, CGs, CHWs	✓													
	Application Needs Post-Assessment	Youth, CGs, CHWs													✓	

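### The schedule ticks the engagement survey (PHE) at weeks 1, 5, 9 and 13-16, but the other T0 and T3 instruments at weeks 0 and 12, so neither a pre-exposure baseline nor an end-of-treatment reading is secured

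*Protocol*

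**What the plan says.** Protocol section 9.0 (Aim 1, Methods) sets out a design of two conditions by four times: "T0: baseline, T1: 1-month follow-up, T2: 2-month follow-up, and T3: 3-month end of treatment". Under Measures, the PHE is named as the means of measuring engagement, and "The PHE survey will be taken via the DWN app at each time point, T0-T3". Section 3.0 (Self-Monitoring Assessments) adds: "At the beginning of the intervention (T0), participants will complete a baseline assessment", which is to be adapted from the PHE, and repeats the engagement questions at T1 to T3.

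Under Aim 2, the needs analysis is to be done before the intervention, with its pre-survey at T0. For the other end: "After completion of the intervention (T3), we will conduct a post-survey to determine if DWN-FIT met their needs and goals". Section 9.0 also states: "Study participation will last 3 months".

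The schedule of measures in section 9.0 has columns for weeks 0 to 12 and one combined column for weeks 13-16. The row "Patient Health Engagement (PHE) Survey" is ticked in columns 1, 5, 9 and 13-16. The needs pre-assessment is ticked in column 0 and the needs post-assessment in column 12.

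**The concern.** One label should point to one time. Here T0 is week 0 for one instrument and week 1 for another, and T3 is week 12 for one and weeks 13-16 for the other. Staff who follow the schedule will collect the PHE at different times from staff who follow the text.

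The first reading matters most. Week 1 is the first treatment week, and families are already randomised. If a family answers late in that week, the value called baseline follows some treatment. In the social support arm it may also follow the very exposure being compared. The last reading has the opposite problem: a four-week column is not one end-of-treatment time point, and families could answer it under different conditions.

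The PHE is the protocol's stated measure of engagement. Aim 1 correlates app behaviour with engagement and asks whether social support enhances it, and the PHE data are meant to serve as preliminary data for later studies. With 16 families, avoidable differences in timing add noise that the sample cannot absorb.

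**Working it through.** **Step 1: read the ticks.** The PHE row and the week header each have 17 cells, so ticks match columns one to one.

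| Instrument | Time point in the text | Column ticked |
|---|---|---|
| Needs pre-survey | T0 | 0 |
| PHE, first | T0 | 1 |
| PHE, second | T1 | 5 |
| PHE, third | T2 | 9 |
| Needs post-survey | T3 | 12 |
| PHE, last | T3 | 13-16 |

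A week-0 column exists and holds the demographics form and the needs pre-survey, but no PHE tick. Nor is there a PHE tick in week 12.

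**Step 2: convert weeks to elapsed treatment time.** Section 3.0 gives week 0 as "Week 0 – DWN-FIT Orientation and Getting Started on the Mobile App" and starts the physical activity modules in week 1, so treatment is counted from the start of week 1. For week w, elapsed treatment is w - 1 weeks at its start and w weeks at its end.

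| Week | Elapsed at start | Elapsed at end |
|---|---|---|
| 1 | 0 | 1 |
| 5 | 4 | 5 |
| 9 | 8 | 9 |
| 13 | 12 | 13 |
| 16 | 15 | 16 |

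At the start of weeks 1, 5, 9 and 13 the elapsed times are 0, 4, 8 and 12 weeks. That reproduces the text's 0, 1, 2 and 3 months in four-week months. The schedule does not say start of week, and the last column runs on to week 16.

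**Step 3: what can precede the first PHE.** Section 3.0 places these in week 1: the first physical activity modules, the start of Fitbit wear and the setting of step goals. The schedule ticks CHW meetings and module review from column 1. Supporters are prompted a day after module release, twice a week for activity, and three times a week for self-monitoring. No sentence orders the PHE against any of these. Exposure before the first PHE therefore ranges from none to a full week.

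**Step 4: what surrounds the last PHE.** Section 3.0 ends the modules with weeks 11-12 and pays supporters for a 12-week period. The last PHE can then fall between 12 - 12 = 0 and 16 - 12 = 4 weeks after treatment. The same column of the schedule still ticks CHW meetings, module review, Fitbit data and the food log, although section 3.0 has the equipment returned when the intervention phase ends. The schedule and the 12-week text do not agree on what happens in weeks 13-16.

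**Step 5: interval between first and last reading.** Shortest: end of week 1 to start of week 13, 12 - 1 = 11 weeks. Longest: start of week 1 to end of week 16, 16 - 0 = 16 weeks. Using week 0 and week 12, as the needs surveys do, would remove most of that spread.

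**The case against.** The best reply is that the schedule can be read to fit the text. Section 3.0 puts T0 at the beginning of the intervention, and week 1 is that beginning. On a start-of-week reading all four ticks land on 0, 4, 8 and 12 elapsed weeks. The Aim 2 text itself describes T3 as after completion of the intervention, so a survey on the first day of week 13 would be consistent with it. This stands as far as it goes. Weeks 5 and 9 are acceptable for T1 and T2, and a post-treatment T3 is not wrong in itself. But the reading depends on a start-of-week rule that the protocol does not state, and it does not explain why the needs surveys with the same labels sit in other columns.

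A reader might infer that the week-1 baseline is contaminated. The document shows only that it may be: a survey on the first day of week 1, before any session, module or prompt, would be clean.

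A reader might also infer that the last PHE has no behavioural data beside it. By the schedule, Fitbit, food log and session items are still ticked in weeks 13-16. Whether they should be is the separate conflict in step 4.

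Two further points limit the stakes. Section 10.0 plans Pearson correlations and two-sample t-tests and states no change-from-baseline analysis of the PHE; a randomised comparison of later scores is not biased by a late baseline. And the primary outcomes are weekly app measures, with the PHE serving as preliminary data. The schedule header also carries an asterisk whose footnote is not in the text available, so a completion rule may exist there.

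**Conclusion.** The point holds as a conflict between text and schedule that leaves two of the four PHE readings undefined. T0 and T3 each map to two columns. The first PHE may follow up to one week of treatment and, in one arm, of social support. The last may fall 0 to 4 weeks after the 12-week programme. This assumes that treatment is counted from the start of week 1 and ends with week 12, as the section 3.0 text has it.

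It is tempting to go further and say that the change in engagement, or the social support contrast, is biased toward no effect by some percentage. That would need the share of any gain already present in week 1 and the share still present in weeks 13-16. The document gives neither, so no size or direction of bias can be claimed.

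The matter should still be settled before enrolment: it concerns the only PHE baseline in a two-by-four design, and a baseline taken too late cannot be recovered afterwards.

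**What to change.** - Move the first PHE tick to week 0, alongside the demographics form and needs pre-survey, and state that it is completed before randomisation. At minimum, state that it precedes the first session, module and supporter message. The order needs to be written down, because the schedule also ticks some daily activity items in column 0, so the column alone does not guarantee a clean baseline.
- Move the last PHE tick to week 12, or to a narrow window shared with the needs post-survey.
- Define T0 and T3 by named week once, and use that definition for every instrument.
- Keep weeks 5 and 9 for T1 and T2 if they are defined as start of week.
- Reconcile the session, module and Fitbit ticks in weeks 13-16 with the 12-week text. If that changes where treatment ends, move both T3 instruments together.

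The cost is an edit to the schedule and a sentence or two of text. The survey is delivered in the app, and the number of administrations stays at four.

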10.0 Data Management

All data will be safeguarded for confidentiality. Families will be assigned an unique identifier (UID) immediately following enrollment into the study. All sources of data will only have reference to the UID number. A file will also be created that links participants to their UID number. This file, consent and assent documents, screening documents, and de-identified data will all be kept in separate, locked file cabinets in the offices of the RAs at the Medical University of South Carolina in the Division of Global and Community Health (MUSC-GCH). Only study research personnel will have access to data that links research data to participant identifiers during the course of the trial.

Data Analysis Strategy

We will utilize a Pearson correlation coefficient (range -1 to 1) to determine the degree of correlation between components of DWN-FIT and engagement and adherence. Each measure will be quantized into a numerical value that can be used to generate the correlation coefficient. To compare the effect of SS on treatment outcomes we will use an independent two-sample t-test ($\alpha = 0.05$) to determine statistical differences between measures such as step count, PA, SM, etc. with respect to treatment condition.

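### Planned correlations of nutrition self-monitoring, PA video views and CBST participation with adherence are pushed upward, because adherence is built from the same app records

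*Protocol*

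**What the plan says.** Protocol section 9.0 states Aim 1 as an evaluation in 16 families "to determine the degree to which the components of the digital intervention are correlated with adolescent-caregiver engagement in healthy behaviors and adherence" to the treatment. The Aim 1 Methods list the app-recorded primary measures. These include "PA and PA video views, frequency and consistency of nutrition SM" and "frequency and consistency of CBST education participation", alongside step count, messaging, session attendance and contingency management (CM) rewards. The analysis is then stated: "In both treatment conditions, we will determine correlation between these measures and our measures of engagement and adherence". The Measures paragraph that follows measures adherence "through comparing the prescribed tasks against the task completed, raw counts (video views, SM entries, PA participation), by each set of participants". Engagement is measured separately, by the Patient Health Engagement (PHE) survey.

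Section 10.0, Data Analysis Strategy, sets a Pearson coefficient "to determine the degree of correlation between components of DWN-FIT and engagement and adherence". It says that each measure will be turned into a number. It does not say how the three counts become an adherence value, and it does not exclude a component from the adherence value that contains it.

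Section 3.0 shows how closely the records match. On self-monitoring: "The DWN will prompt the participants daily to use the SM feature of the mobile app to complete an assessment". That daily assessment covers PA tasks and learned skills, with a food log given as an example. In addition, "The DWN will also conduct weekly assessments, initially only asking participants to weigh themselves and record their body fat". CBST content is delivered as videos, the PA workout demonstrations are categories of CBST video, and the number of workouts follows goals set in the weekly assessment.

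**The concern.** When a count is correlated with a score that contains it, part of the coefficient comes from the count being on both sides. If adherence is kept task by task, a count is correlated with a rescaling of itself. Either way r is positive in expectation for families whose behaviours are unrelated.

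The Aim 1 question is whether the components go with adherence. For the overlapping pairs, a high r may say no more than how adherence was scored. A reader could take it as evidence that, for instance, self-monitoring goes with following the rest of the treatment, and could carry that into the larger trial that the Protocol says this study is meant to support.

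**Working it through.** The Protocol gives no expected correlation, power or scoring figure for this analysis, so there is nothing to reproduce. The check has two parts: where the records overlap, and what the overlap does under stated assumptions.

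**Overlap, measure by measure (sections 3.0 and 9.0)**

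| Measure to be correlated | Adherence count sharing its record | Match |
|---|---|---|
| Nutrition SM frequency | SM entries | Close; SM entries also include weekly and perhaps other daily items |
| PA video views | Video views | A subset of all views |
| CBST participation | Video views | Close if taken from views; looser if taken from time on modules, which the schedule of measures also records |
| PA | PA participation | Same record, but judged against a self-set goal |
| SM and CBST consistency, CM rewards, step count | Indirect | Partial |
| PHE score, messaging, attendance | None of the three listed counts | No overlap |

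**If adherence is a composite.** Assume three parts of equal variance with common correlation ρ.

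- Own part included: r = (1 + 2ρ)/√(3 + 6ρ).
- Own part left out: r = 2ρ/√(2 + 2ρ).

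| ρ | Own part included | Own part left out |
|---|---|---|
| 0 | 1/√3 = 0.58 | 0 |
| 0.2 | 1.4/√4.2 = 0.68 | 0.4/√2.4 = 0.26 |
| 0.4 | 1.8/√5.4 = 0.77 | 0.8/√2.8 = 0.48 |

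With independent parts of unequal SD, r = s₁/√(s₁² + s₂² + s₃²). SDs of 1, 2, 2 give 1/3 = 0.33, and SDs of 2, 1, 1 give 2/√6 = 0.82. In 40,000 simulated trials with equal SDs and ρ = 0, r was positive in 99% with 16 families and in 95% with the 8 families of one arm. With the own part left out it was positive in 50%.

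**If adherence is kept task by task.** Independent entry types and equal SDs of completion rate are assumed.

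- Nutrition SM frequency against SM entries, fixed prescription of 12 × 7 = 84 daily entries: r = 1.00.
- The same with 12 weekly entries added: 84/√(84² + 12²) = 0.99.
- The same if the daily assessment is logged as two separate entry types: 84/√(2 × 84² + 12²) = 0.70. With three types: 84/√(3 × 84² + 12²) = 0.58.
- PA video views as a share s of all views: r = s/√(s² + (1 − s)²). The share is not given. Two weeks of PA education in 12 suggest s = 1/6, and workout demonstrations add an unknown number. For s = 1/6, 1/4, 1/2 and 3/4, r = 0.20, 0.32, 0.71 and 0.95.
- CBST participation from views against a fixed prescription: r = 1.00. From time on modules, with an assumed coefficient of variation of minutes per view of 0.2 to 0.5: r = 0.48 to 0.90 (simulation).

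**PA.** The workout count is divided by a goal that differs between families. With assumed goals between 1 and 5 workouts a week, simulated r of the count with its own goal proportion was 0.48 to 0.90 if goals are unrelated to completion. It was 0.15 to 0.88 if goal and completion correlate −0.5, and −0.05 to 0.88 at −0.7. Upward distortion is therefore probable for PA but not assured.

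**Partial overlaps, composite score, independent behaviours.** CM rewards pay $50 for attendance and $10 for each of four goals, three of which match the adherence counts. Before bonuses, r = (3 × 10)/√((50² + 4 × 10²) × 3) = 0.32. Step count shares workouts done while wearing the Fitbit. With assumed steps per workout and background variation, r with workouts is 0.061 to 0.43, and multiplying by 0.577 gives 0.04 to 0.25.

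**The case against.** The strongest reply is that the Protocol never says the three counts are summed, and that building the score may be left to a statistical analysis plan. This stands as far as size goes: no single figure can be given. It does not remove the point, because the Protocol itself fixes the overlapping source counts, the pairs to be correlated and the statistic. A plan that follows this text inherits the overlap.

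A related reply is that under task-by-task scoring only the own-task pairs are affected. That is correct. SM frequency against video or workout adherence shares no SM record and stays usable, and an own-task r of 1.00 would probably be recognised for what it is.

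Unrelated behaviours are also an unrealistic baseline, since the same families use one app and are paid weekly for several of these tasks. The comparison at ρ = 0.4 (0.77 against 0.48) is then fairer than 0.58 against zero. The direction holds, but the distortion is smaller.

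Finally, this is a 16-family feasibility study. A reader might infer that the overlap will produce false significant results. The documents do not support that: the 0.05 level is stated for the t-test only, and no test of r is planned.

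**Conclusion.** The point holds for nutrition SM frequency, PA video views and CBST participation, and probably for PA. For these, the planned r with adherence is pushed upward by shared records and cannot answer whether the component goes with adherence to the rest of the treatment. That the overlap exists is clear from the text. Its size is not: the figures above depend on assumed weights, variances, video shares and ways of logging entries. The value of 0.58 is an illustration and not an estimate for this trial.

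A reader might go further and infer that the whole Aim 1 correlation analysis is circular. It is not. The PHE correlations rest on a separate survey, messaging and attendance are not among the three listed adherence counts, and the between-arm t-tests do not use these correlations. No decision rule or sample size depends on them either. The change should be made before analysis, but nothing in the conduct of the study turns on it.

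**What to change.** Amend the Aim 1 Methods and Measures in section 9.0 and the Data Analysis Strategy in section 10.0 so that no component is correlated with an adherence value that contains it.

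- If adherence is a composite, use a leave-one-out score: the proportion of prescribed tasks completed, without the task type that the component supplies. Leave out SM entries for nutrition SM frequency and consistency; all video views for both PA video views and CBST participation; and workouts for PA.
- If adherence is kept task by task, report only the cross-task correlations.
- Report each component's own completed-to-prescribed proportion, and CM rewards, descriptively.
- Report the step-count correlation with a note that workouts contribute to both sides.
- Keep the PHE, messaging and attendance correlations as planned.

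The cost is a redefinition of derived variables, with no new data. There will be fewer and smaller correlations, and each leave-one-out score rests on two task types instead of three. Because those scores differ between components, the coefficients are not on a common scale and should not be used to rank components. For PA, the leave-one-out score removes the shared record but keeps related content (PA videos and PA items in SM entries), and the report should say so.
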